5.5.4. Quality of life variables

5.5.4.1. Change from baseline by visit up to Extension EOS in SF-36v2™ Health Survey domain and component scores

The SF-36v2™ instrument is a generic health related quality of life assessment provided by the Medical Outcomes Trust, Boston, USA.

It contains 36 items measuring health across eight areas or domains: Physical Functioning (PF, 10 items: #3a – #3j); Social Functioning (SF, 2 items: #6 & #10); Role Limitations due to physical problems (RP, 4 items: #4a – #4d); Role Limitations due to emotional problems (RE, 3 items: #5a – #5c); Mental Health (MH, 5 items: #9b – # 9h); Vitality (VT, 4 items: #9a – #9i); Bodily Pain (BP, 2 items: #7 & #8) and General Health perceptions (GH, 5 items: #1, #11a – #11d) and an additional item on reported Health Transition to perceive changes in health status in the past 12 months (HT, 1 item: #2).

In addition, Physical and Mental Component Summary (PCS and MCS) measures are calculated based on aggregate domain scores.

For each of the eight domains, scores will be coded, summed and transformed to generate a score from 0 (worst possible health state) to 100 (best possible health state). These domain scores as well as PCS and MCS will then be standardized to Z scores and then again will be transformed to create norm based scoring also known as t-scores. Scoring will be performed via licensed vendor QualityMetric using ProCore software. QualityMetric's 1998 US population weights will be used to generate norm-based scores, which is consistent with methods in core study AC 058B301 (OPTIMUM). Weighting for norm-based score calculation is embedded in the ProCore Software.

The SF-36v2TM is completed by the subject on an electronic device at defined visits up to extension EOS (see Section 6.12).

5.5.4.2. Analysis of SF-36v2™ Health Survey

Quality of life analysis based on the SF- $36v2^{TM}$ will be performed on the Combined period and Extension period using EXTS.

The eight normative (t-scores) domain scores, PCS and MCS will be summarized descriptively over time. In addition, the change from core baseline as well as change from extension baseline will be summarized by analysis visits.

5.5.5. Biomarkers

No biomarker analysis is applied in this study.

5.5.6. Subgroups analysis

To understand the change in some safety profiles after EOT, the following "Post-treatment DMT" subgroup is defined and the analysis by subgroup will be performed.

- Sub-population included in the analysis: This subgroup analysis includes the subjects who have an EOS visit and the start date of the EOS visit is at least 5 days after the EOT date
- Post-treatment DMT subgroup definition: A patient in the above-defined sub-population will be assigned to the "Any DMT" category if meeting all the following conditions:
 - 1) There is a record in CMDECOD in SDTM.CM for any of the therapies listed in Section 6.5.1.4, and the medication is administered systemically via the following routes: Intravenous (IV), Oral, Subcutaneous (SC), Intramuscular (IM).
 - 2) The corresponding CMSTDTC is on or after the EOT date, or CMSTDTC is before EOT date and CMENDTC is after the EOT date, or CMSTDTC is before EOT date and CMENDTC is missing indicating that the medication is ongoing at EOS.

Otherwise, the patient is assigned to the "No DMT" category.

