1.2.3.1. End-of-treatment visit

The EOT visit will take place at Week 240 or at the time ponesimod is commercially available for treatment of MS in the subject's country (whichever occurs first). The EOT visit should preferably take place 1 day after the last dose of study treatment but no later than 14 days after the last dose of study treatment. The EOT visit may take place in case:

- of premature discontinuation of study treatment for subjects meeting the study specific criteria for permanent discontinuation of study treatment;
- the sponsor decides to stop the extension study;
- the subject or the investigator decides to discontinue the study treatment;
- ponesimod is commercially available for the treatment of MS in the subject's country.

In some countries, additional reimbursement negotiations and central formulary approvals will be needed before ponesimod becomes available. In this case, subjects participating in the AC-058B303 study can continue to receive ponesimod until ponesimod is available in their respective country, or for a maximum of 240 weeks. Subjects will get access to the study drug for a maximum of 240 weeks*. If ponesimod becomes available locally before the end of the 240 weeks in the AC-058B303 extension study, then subjects will be considered as having completed the extension study and will be switched to commercially available supply if they wish to continue ponesimod treatment. For these subjects, the switch to commercially available ponesimod should occur at the EOT visit, and commercially available ponesimod may be initiated on the day following last intake of study treatment.

[figure not shown]
*except for subjects in Ukraine where the maximum treatment duration will be 288 weeks (or not later than preplanned global Last Subject Last End of Treatment in Q4 2023)

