5.1.1.4. Post-treatment analysis Period

This period is defined for post-treatment analyses for certain safety variables. It includes all available data from extension EOT date (defined in Section 5.1.9.3) + 16 days (inclusive) in the extension study up to the extension EOS.

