5.1.9.3. Extension End-of-Treatment (EOT) date

If a subject is considered to have prematurely discontinued treatment in the extension study, the date of last study drug intake in the extension study corresponds the end of treatment date, derived as:

• The maximum of [End date up-titration on eCRF page 'Up-titration Summary', Treatment end date on eCRF page 'Up-titration Ponesimod'; Treatment end date on eCRF page 'Maintenance

- Ponesimod']; this is derived in the SDTM.DM dataset as the 'Date/Time of last study treatment' (RFXENDTC);
- If missing based on the above, then the treatment termination date as recorded on the RAVE primary form is taken. This is derived in the SDTM.DS dataset as 'Start Date/Time of Disposition Event' (DSSTDTC) where the 'Subcategory for Disposition Event' (DSSCAT) is 'TREATMENT TERMINATION' and the 'Standardized Disposition Term' (DSDECOD) is not 'COMPLETED'.

If a subject is considered to have completed treatment as per protocol, the date of last extension study drug intake corresponds to the minimum of:

- Treatment end date on extension study eCRF page 'Maintenance Ponesimod' corresponding to the record "Completed as per protocol"; this is derived in the SDTM.DM dataset as the 'Date/Time of last study treatment' (RFXENDTC);
- If missing based on the above, then the treatment termination date as recorded on the RAVE primary form is taken. This is derived in the SDTM.DS dataset as 'Start Date/Time of Disposition Event' (DSSTDTC) where the 'Subcategory for Disposition Event' (DSSCAT) is 'TREATMENT TERMINATION' and the 'Standardized Disposition Term' (DSDECOD) is 'COMPLETED';

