5.4.2.3.1. Adverse events

Unless otherwise specified, all the AE summaries described below are produced for the Combined Analysis Period (only for subjects included in the SAF who were initially treated with ponesimod 20 mg in the core study) and for the Extension Analysis Period by core study treatment and overall, using the EXTS.

An overview of TEAEs is presented, per study treatment group, as the number and percentage of subjects having any AE, any severe AE, any drug-related AE, any AE leading to study drug discontinuation, any SAE, any drug-related SAE, or any fatal SAE. Similarly, an overview of TEAEs per 100 subject-years is also presented.

The following summary tables will be created to present the frequency and percentage of subjects with any AE, an AE in each primary SOC, and each individual AE (preferred term). SOCs are sorted by descending order of frequency in the ponesimod arm. If the frequencies of SOCs are the same, alphabetical order is used. The same rule applies for preferred terms within SOC:

- All AEs;
- TEAEs;
- TEAEs per 100 subject-years; TEAEs with onset on Day 1 of a re-initiation (all re-initiations summarized together, for subjects with at least one re-initiation), Extension Analysis Period only:
- TEAEs leading to permanent discontinuation of study treatment;
- TEAEs considered to be related to study drug;
- Severe TEAEs;
- Post-treatment AEs (subjects that entered the period between EOT date + 16 and EOS), Extension Analysis Period only.

The following summary tables will also be produced, presenting the frequency and percentage of subjects with any AE, and each individual AE (preferred term) by descending frequency:

CONFIDENTIAL – FOIA Exemptions Apply in U.S.

- TEAEs;
- TEAEs per 100 subject-years;
- TEAEs leading to permanent discontinuation of study treatment;

• TEAEs reported in \geq 5% of subjects in any group (after rounding into the 1st decimal in percentage, e.g. an event occurring in 4.955% of subjects will be rounded to be 5.0% and therefore be included in this summary table).

The following summary tables will also be produced, presenting the frequency and percentage of subjects with any AE, and each individual AE (preferred term) by maximum intensity:

• TEAEs.

AEs (preferred terms) reported more than once in a subject during the period summarized are counted once in frequency tables. Percentages are based on the SAF (ponesimod subjects) or on the EXTS as applicable.

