5.5.3. Pharmacodynamics

The pharmacodynamic (PD) marker evaluated in this study is Peripheral lymphocyte counts, which were measured as part of the clinical laboratory hematology tests.

To capture the abnormality in lymphocyte counts, among the treatment-emergent-flags abnormal values, the lowest lymphocyte counts through all post-baseline assessments are further categorized into the following categories. This will be done separately for combined period and for extension period.

- $< 0.2 \times 10^{9}/L$;
- $\geq 0.2 \times 10^{9}/L < 0.5 \times 10^{9}/L$;
- $> 0.5 \times 10^{9}/L < 0.8 \times 10^{9}/L$;
- $\geq 0.8 \times 10^{9}/L < 1.0 \times 10^{9}/L;$
- $> 1.0 \times 10^{9}$ L.

The following analyses will be conducted:

- Peripheral lymphocyte counts and the associated percentage change from core baseline by visit and by treatment group during combined period using SAF, along with a line graph to present the percent change from core baseline in peripheral lymphocyte counts by treatment group over visit. Note that only the following nominal visits will be visualized in the plot: Core period -- Baseline, Week 2, Week 4, Week 12, Week 24, Week 48, Week 72, Week 96, Week 108, D15 FU, D30 FU; Extension period -- Baseline, Week 2, Week 4, Week 12, Week 24, Week 48, Week 96, Week 144, Week 192, Week 240, Week 288, extension EOT, extension EOS.
- Peripheral lymphocyte counts and the associated percentage extension change from baseline by visit and by treatment group during extension period using EXTS, along with a line graph to present the percent change from core baseline in peripheral lymphocyte counts by treatment group over visit.
- Incidence of treatment-emergent marked abnormalities for blood lymphocyte counts for combined period using SAF and for extension period using EXTS.

In addition, to understand the change in lymphocyte counts after EOT, the following analyses will be done for subjects who continue any DMT after EOT date versus subjects who have no DMT after EOT date:

- Peripheral lymphocyte counts over the following visits: Core baseline, Extension Baseline, Extension EOT, Extension EOS visit and the change from Core baseline using EXTS.
- A line graph to present the percent change from core baseline in peripheral lymphocyte counts over the following visits: Core baseline, Extension Baseline, Extension EOT, Extension EOS.

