Con = concomitant; eCRF = electronic Case Report Form; MS = multiple sclerosis; Prev = previous; STS = study treatment start. For subjects randomized but not treated in the core study the randomization date is used instead of the core STS. For subjects enrolled but not treated in the extension study, the enrollment date is used instead of the extension STS.

Concomitant medications entered on the eCRF page "Ongoing Concomitant Medication from AC-058B301" are considered to be concomitant in both the Combined and Extension Analysis Periods. Concomitant medications entered as "Ongoing at EOS" on the core study eCRF page are considered to be concomitant in both the Combined and Extension Analysis Periods for subjects that entered the extension, even if a corresponding "Ongoing Concomitant Medication from AC-058B301" has not been completed for the extension.

In this study subjects are allowed to switch to commercial ponesimod prior to week 240 / week 288, with the ponesimod medication documented in the concomitant medication eCRF page. In this regard, the commercial ponesimod is considered as post-EOT medication unless there is evidence showing that the commercial ponesimod is taken prior to EOT date. In case of partial CM start date, the commercial ponesimod is considered as a post-EOT medication if the month and/or year is the same as the EOT date. The commercial ponesimod is considered as a post-EOT medication in case of completely missing start date in the CM dataset.

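### The 'Any DMT' group in the post-EOT lymphocyte and lung-function analyses mixes continued ponesimod with other therapies, and the 5-day entry rule may make 'No DMT' understate change after treatment

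*SAP*

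**What the plan says.** **The groups.** SAP section 5.5.6 defines the sub-population by the entry rule "the start date of the EOS visit is at least 5 days after the EOT date". A subject joins 'Any DMT' when "There is a record in CMDECOD in SDTM.CM for any of the therapies listed in Section 6.5.1.4", given by a systemic route and either started on or after EOT or running across it. Everyone else is 'No DMT'. Section 5.5.3 applies this to lymphocytes, comparing "subjects who continue any DMT after EOT date versus subjects who have no DMT after EOT date", and section 5.4.3.4.2 does the same for pulmonary function tests (PFTs). Both show core baseline, extension baseline, EOT and EOS, without regard to core treatment. The stated aim in each is to understand change after EOT.

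**Ponesimod as a DMT.** Table 9 in section 6.5.1.4 lists ponesimod among the other agents without any classes. Section 1.2.3.1 says that "commercially available ponesimod may be initiated on the day following last intake of study treatment". Section 1.2.4 keeps the EOS visit and its assessments for subjects who switch. Section 6.13.1 adds that "the commercial ponesimod is considered as post-EOT medication unless there is evidence showing that the commercial ponesimod is taken prior to EOT date".

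**The time windows.** EOT is tied to the last dose: section 5.1.9.3 states that "the date of last study drug intake in the extension study corresponds the end of treatment date" for premature discontinuations, and it also uses last intake for completers. Section 5.1.6 counts assessments up to 15 days after treatment end as treatment-emergent. Section 5.1.1.4 starts the post-treatment period at EOT + "16 days (inclusive) in the extension study up to the extension EOS". Section 1.2.4 plans EOS for days 30-44.

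**Adverse events.** Section 5.4.2.3.1 plans a frequency table of "Post-treatment AEs (subjects that entered the period between EOT date + 16 and EOS), Extension Analysis Period only", with no split by later therapy.

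**The concern.** An analysis of change after stopping a drug needs to know who stopped. Subjects who move straight to commercial ponesimod have changed supply, not treatment. Placing them with subjects who left ponesimod for another agent gives one curve that averages two different situations. The balance between them is set by how many subjects had access to commercial drug.

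Two smaller points bear on the other displays. The 5-day floor lets a value from an interval that the SAP elsewhere treats as treatment-emergent stand as the value after treatment. The post-treatment adverse event table does not distinguish subjects still taking ponesimod from subjects who are off it. At stake is how a reader interprets the post-EOT lymphocyte and PFT curves and that table. No hypothesis test depends on them.

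**Working it through.** The plan gives no figure to reproduce here. The check follows the definitions through and then gauges size under stated assumptions.

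**1. Does a switcher land in 'Any DMT'?** Take a subject whose last study dose is on day 0 and who starts commercial ponesimod on day 1, as section 1.2.3.1 permits. The drug is in Table 9, is taken orally, and starts after EOT, so both conditions in section 5.5.6 are met. Section 1.2.4 gives the subject an EOS visit. The subject therefore counts in 'Any DMT' with no off-drug interval, and no ponesimod stratum is defined.

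**2. What does the pooled mean show?** Let p be the share of 'Any DMT' on commercial ponesimod (assumed to show no recovery) and r the share of full recovery reached by the rest. Mean recovery = (1 - p) × r. The SAP gives neither p nor r, so both are assumed.

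| p | r = 0 | r = 0.5 | r = 1 |
|---|---|---|---|
| 0.25 | 0 | 0.375 | 0.75 |
| 0.50 | 0 | 0.25 | 0.50 |
| 0.75 | 0 | 0.125 | 0.25 |
| 0.95 | 0 | 0.025 | 0.05 |

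The range is 0 to 0.75, and one value can arise in different ways. A mean of 0.25 fits half the group on ponesimod with half recovery in the rest, (1 - 0.50) × 0.5. It equally fits three quarters on ponesimod with full recovery in the rest, (1 - 0.75) × 1. The curve alone cannot tell these apart.

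**3. How does the 5-day floor sit against the SAP's own windows?** All are counted from the last dose.

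- Day 5 lies 15 - 5 = 10 days inside the treatment-emergent window.
- It comes 16 - 5 = 11 days before the post-treatment period begins.
- It comes 30 - 5 = 25 days before the earliest planned EOS.

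The EOT visit may itself fall up to 14 days after the last dose (section 1.2.3.1). One subject's EOT value could therefore be further off drug than another subject's EOS value.

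**4. How much could early visits dilute 'No DMT'?** Let f be the fraction of EOS visits on days 5-15 and g the share of eventual recovery reached by then. Share of recovery kept = 1 - f × (1 - g). Again f and g are assumed.

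| f | g = 0 | g = 0.25 | g = 0.5 | g = 0.75 |
|---|---|---|---|---|
| 0.02 | 0.98 | 0.985 | 0.99 | 0.995 |
| 0.05 | 0.95 | 0.963 | 0.975 | 0.988 |
| 0.10 | 0.90 | 0.925 | 0.95 | 0.975 |
| 0.20 | 0.80 | 0.85 | 0.90 | 0.95 |

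The group keeps 80% to 99.5%. The signal is weakened, not lost.

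**5. Can a ponesimod user fall into 'No DMT'?** Every timing route in section 5.5.6 compares a start date with EOT. Read literally, a record without a start date meets none of them and goes to 'No DMT'. Section 6.13.1 treats commercial ponesimod with a completely missing start date as post-EOT, but section 5.5.6 does not invoke that rule.

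**6. Adverse events.** The period from EOT + 16 days to EOS is off study supply. For a switcher it may still be on ponesimod, and the planned table does not separate the two.

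**The case against.** The strongest reply is that reversal would be read from 'No DMT', which is shown separately at all four time points. Recorded commercial ponesimod users and users of every other listed DMT are excluded from it, so pooling within 'Any DMT' leaves it untouched. This stands. A reader might infer that the analyses cannot show whether effects reverse; the documents do not support that. The SAP does not use the word reversal either, and section 2 makes all analyses exploratory.

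Second, 5 days is a floor and not the usual timing. EOS is planned for days 30-44, and the EOT visit preferably falls one day after the last dose. The SAP uses EOT + 15 days to attribute safety data and never calls it a washout. It gives no recovery time that would make day 16 the right boundary on pharmacological grounds. This also stands, so the case for day 16 is consistency within the SAP and nothing more.

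Third, section 6.5.2.1 already summarises post-treatment DMTs and lists all DMTs by subject, so the mix is visible. That is true, but these outputs do not link the agent to the lymphocyte or PFT result.

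Fourth, post-treatment events are defined by the last study dose, so the adverse event table matches its definition, and both events and DMTs are listed by subject. A split remains useful to anyone reading the table as off-drug safety. A reader might also suppose that post-treatment event rates are affected, but the rates per 100 subject-years are planned for treatment-emergent events, while this table gives frequencies and percentages.

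**Conclusion.** The point holds in limited form. 'Any DMT' as defined averages continued ponesimod with a change to other agents, so its course from EOT to EOS shows neither persistence nor reversal. Under the assumed ranges its mean recovery could lie anywhere from 0 to 0.75 of full. This rests on the SAP's definitions; only the size depends on assumed values.

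'No DMT' remains interpretable. It may understate change after treatment through EOS visits on days 5-15, with 80-99.5% of recovery kept under the assumed ranges. The true share of such visits is not stated and is probably small given the planned EOS timing. Commercial ponesimod records without a start date could add to the dilution.

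The groups are formed by what happened after EOT, so any contrast between them is descriptive. The documents do not show that other S1P modulators must form their own class: Table 9 has no classes, and further splitting would thin the groups. This is an inexpensive improvement to a secondary descriptive display.

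**What to change.** 1. In section 5.5.6, and so in sections 5.4.3.4.2 and 5.5.3, report three groups: commercial ponesimod continued, other DMT, and no DMT.
2. State in section 5.5.6 that the section 6.13.1 rule for partial or missing start dates of commercial ponesimod applies, so that these users are not assigned to no DMT.
3. Raise the 5-day floor to EOT + 16 days to match section 5.1.1.4. Alternatively, keep it with a stated reason and add a sensitivity analysis limited to EOS at EOT + 16 days or later.
4. Show the post-treatment adverse event frequency table in section 5.4.2.3.1 with and without commercial ponesimod.

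Drug names and dates are already needed to form the present groups, so no new data are required. The cost is SAP wording, programming, smaller groups and, if the floor is raised, the loss of any EOS visits on days 5-15.

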1.2.4. Safety follow-up

For an individual subject, End-of-Study (EOS) is reached when treatment and safety FU have been completed. The EOS Visit should be performed 30-44 days after the permanent discontinuation of study treatment. If during study treatment interruption, the subject fulfills the criteria for premature discontinuation, the EOS visit should be scheduled as soon as possible after the decision to prematurely discontinue has been taken.

The EOS visit and all assessments will also be conducted for subjects who have switched to commercially available ponesimod.

The overall AC-058B303 study design is depicted in Figure 1.

EOT = End-of-Treatment; EOS = End-of-Study; V = Visit; FU = Follow-up; - - - = no treatment.

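### The post-treatment DMT grouping in SAP 5.5.6 does not require the DMT to start before the EOS assessment, and it has no rule for a DMT other than ponesimod with a missing start date

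*SAP*

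**What the plan says.** Section 5.5.6 first fixes who is analysed, counting from EOT: "This subgroup analysis includes the subjects who have an EOS visit and the start date of the EOS visit is at least 5 days after". Within that population, a subject is Any DMT if a therapy listed in Section 6.5.1.4, given by a systemic route, meets one of three date arms. The first two are "The corresponding CMSTDTC is on or after the EOT date, or CMSTDTC is before EOT date and CMENDTC is after the EOT date". The third is "CMSTDTC is before EOT date and CMENDTC is missing indicating that the medication is ongoing at EOS". For everyone else the rule is "Otherwise, the patient is assigned to the" No DMT category.

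The grouping is used twice. Section 5.5.3 compares lymphocyte counts "for subjects who continue any DMT after EOT date versus subjects who have no DMT after EOT date", and the display is "Peripheral lymphocyte counts over the following visits: Core baseline, Extension Baseline, Extension EOT, Extension EOS visit and the change from Core baseline using EXTS". Section 5.4.3.4.2 does the same for the lung-function parameters. Section 1.2.4 times the last of these visits: "The EOS Visit should be performed 30-44 days after the permanent discontinuation of study treatment".

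On missing start dates, Section 6.13.1 has a rule for one drug: "The commercial ponesimod is considered as a post-EOT medication in case of completely missing start date in the CM dataset". It also treats a partial start date for commercial ponesimod as post-EOT when the month and/or year agrees with EOT. Ponesimod is among the DMTs of Table 9 in Section 6.5.1.4.

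**The concern.** The displays are meant to show what happens to lymphocytes and lung function after study drug stops, with and without a further DMT. The comparison is read at the EOS visit, so what matters is whether the subject took a DMT between EOT and the EOS tests. A drug first taken after a test cannot affect its result.

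The rule asks only whether the DMT started on or after EOT. The 5-day requirement limits the timing of the visit relative to EOT, not the timing of the DMT relative to the visit. An off-drug subject can therefore be moved into the treated curve by a prescription written at the EOS visit. In the other direction, a DMT other than ponesimod with no recorded start date satisfies no arm, and the default places its user in the off-drug curve. Both errors would tend to understate the difference between the curves.

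**Working it through.** The SAP states no figure for this point, so there is none to reproduce. The check applies the written rule to test records and compares the result with exposure before the EOS tests.

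**Inputs.** Day 0 is the EOT date. EOS is placed at day 30 and at day 44, the ends of the window in Section 1.2.4. The three date arms and the default come from Section 5.5.6, and the commercial-ponesimod rule from Section 6.13.1. The results are the same for both EOS days.

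| Record | 5.5.6 as written | With 6.13.1 | Bounded at EOS, with a missing-start rule |
|---|---|---|---|
| Commercial ponesimod from day 1 | Any | Any | Any |
| Other DMT, starts the day before EOS | Any | Any | Any |
| Other DMT, starts on the EOS day | Any | Any | **No** |
| Other DMT, starts 5 days after EOS (if recorded) | Any | Any | **No** |
| Other DMT, start missing, ongoing | No | No | **Any** |
| Other DMT, start missing, ended 10 days after EOT | No | No | **Any** |
| Commercial ponesimod, start missing | No | Any | Any |
| DMT started and ended before EOT | No | No | No |

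**Does another section supply the limit or the missing rule?**
- Section 6.5.1.2 defines post-treatment DMT as starting on or after EOT, also without an upper limit.
- Section 6.5.1.3 has a missing-start rule, but that section excludes DMTs.
- Table 14 in Section 6.13.1 sorts therapies only into previous or treatment-concomitant and is not tied to the grouping of 5.5.6.

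**Can an EOS-day start reach the data?** Yes. Table 13 in Section 6.12 schedules the collection of concomitant medications at EOS.

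**Direction of the effect.** Let q be the share of Any DMT subjects not exposed before the EOS tests, and r the share of No DMT subjects who were exposed. Let E and U be the mean outcomes of the truly exposed and unexposed, and suppose misplaced subjects have the mean of their true group. Then:

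- Any DMT mean = (1 − q)E + qU
- No DMT mean = (1 − r)U + rE
- Difference = (1 − q − r)(E − U)

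The shares below are assumed, because the SAP gives none:

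- q = 5%, r = 0: 1 − 0.05 − 0 = 0.95
- q = 10%, r = 5%: 1 − 0.10 − 0.05 = 0.85
- q = 20%, r = 10%: 1 − 0.20 − 0.10 = 0.70

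These factors show the direction and how the effect scales. They do not estimate what will occur in this study.

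**The case against.** The strongest reply has four parts.

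**Late starts may hardly occur in the data.** No visit is scheduled after EOS, safety follow-up ends there, and 5.5.6 itself reads a missing end date as ongoing at EOS. A reader might infer that DMTs begun well after EOS contaminate the treated curve. The SAP does not support that, because it does not show that such starts are recorded. If recording stops at EOS, only starts on the EOS day remain. This part of the reply stands and limits the point.

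**Commercial ponesimod is covered.** A reader might also infer that subjects still taking ponesimod fall into the off-drug curve when the start date is missing. Section 6.13.1 says otherwise. It places commercial ponesimod after EOT when the start date is missing, and also when a partial date agrees with EOT. Since Section 1.2.3.1 allows commercial supply from the day after the last study dose, most switchers to it should not be affected by the missing upper limit either. What remains is that 5.5.6 does not point to 6.13.1 and, read alone, gives the opposite answer.

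**Any cut-off is partly a convention.** A DMT started the day before EOS would still count as treated under the proposed bound, although it has had little time to act. That is true. But a bound at the EOS visit removes the cases in which an effect is impossible, and the wording of the third arm suggests that exposure up to EOS is what was intended.

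**Little depends on these displays.** Section 2 states that there are no hypotheses and that all analyses are exploratory. The two displays disregard treatment group and carry no test. This stands and sets the severity.

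**Conclusion.** The point holds and is minor. As written, 5.5.6 classes as treated a subject who was off drug at the EOS tests and started a DMT that day. It classes as untreated a subject on a listed DMT other than ponesimod whose start date is completely missing, even when that drug is ongoing at EOS. No other section corrects either case.

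The expected effect is a weaker contrast between the curves at EOS. Its size cannot be derived, because the SAP gives neither the number of starts on or after the EOS day nor the number of missing start dates. The factor 1 − q − r also assumes that misplaced subjects resemble their true group. That may fail, because Any DMT pools many agents. No error rate is affected, and no main efficacy or safety result uses this grouping.

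**What to change.** Make three changes in Section 5.5.6:

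1. In condition 2, require the DMT start date to be before the EOS visit date. Assign subjects whose first post-EOT DMT starts on or after that date to No DMT.
2. Refer to Section 6.13.1 for commercial ponesimod with a missing or partial start date, so that the two sections give one answer.
3. For any other listed DMT with a missing start date, assign Any DMT when the end date is after EOT or the record is ongoing at EOS.

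The third rule assumes that such a drug was started before the EOS tests. A footnote giving the number of subjects classified this way would let the reader judge that assumption. The cost is a few clauses and one date check in programming, with no new data.
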